**Liposomal Bupivacaine in Adductor Canal Blocks Before Total
Knee Arthroplasty Leads to Improved Post-Operative
Outcomes: A Randomized Controlled Trial**

NCT: NCT04910165

Date: 4/01/2020

Purpose: To explore the effectiveness of Exparel (liposomal bupivacaine) in Adductor Canal Blocks for peri-operative pain control following a total knee arthroplasty (TKA) procedure: reduce opioid requirement use postoperatively, reduce pain scores postoperatively, provide earlier mobilization, and decrease length of hospital stay.

Methods: Our double blinded (patient and orthopaedic department) prospective randomized controlled study will collect 100 patients who receive an adductor canal block with Exparel and compare it with 100 patients who received an adductor block with ropivacaine. Each patient will be randomized using an online number generator. Only the anesthesiologist will be privy to which medicine was used in the block, with both the patient and the surgeon being blinded. Patients will either receive Exparel 20 ccs with 5 ccs of 0.5% bupivacaine in the adductor canal block and 20 ccs of 0.2% Ropivacaine in the iPACK block (Exparel group) or 25 ccs of 0.2% ropivacaine in the adductor canal block, and 20 ccs of 0.2% ropivacaine in the iPACK block (control group). These blocks will be placed in the pre-operative holding area under ultrasound guidance. Intraoperatively, patients will receive a spinal anesthetic utilizing 0.75% hyperbaric bupivacaine at the L3-4 or L4-5 levels and a propofol infusion for IV sedation. Patients will be seen in the PACU area, where pain scores and oral morphine equivalents (OME) are calculated. Patient will be seen on POD 1 to discuss expectations of pain control and goals for pain management (i.e. use of multimodal pain regimen and goals to decrease opioid use). Pain scores and OMEs will be calculated for POD 0-3. Progress notes in EPIC and patient interview will also disclose if patient had PT/mobilization early. We will finally review EPIC encounter for length of admission (date of admission to date of discharge), complication rates from the block, and readmission for pain.

Inclusion Criteria: Undergoing unilateral primary TKA for a diagnosis of knee osteoarthritis without additional concomitant procedures

Exclusion Criteria: Not undergoing a TKA after initially signing up for surgery, if they do not undergo spinal analgesia (due to medical contraindications or a failed attempt by the anesthesiologist), if the proper suspension or local anesthetic mixture is not utilized for the block due to physician error, or if they voluntarily drop out during the study period.

Risks and Benefits of Exparel:

Risks-side effects of Exparel include N/V, HA, and dizziness. As with any local anesthetic, more serious risks may include local anesthetic toxicity (neurologic and cardiac symptoms, cardiac arrest)

Benefits-Improved peri-operative pain control: we aim for a modest reduction of opioid use during the postop period (<60 oral morphine equivalents during first 2-3 days), decrease length of hospital stay (by 0.5-1 day), and reduction in pain scores

Study Visits:

Pre-op - Patient seen in Ortho office for initial consent to TKA and to fill out questionnaire (see attached). **Day of Surgery**- patient consented in the preoperative holding area with anesthesia, where blinding process occurs. Adductor canal block placed preoperatively.

After surgery- We will visit the patient in PACU to ask about pain scores and determine amount of opioid IV used in PACU. We will also visit the patient in POD 1 to discuss expectations of pain control. We will also look in EPIC to determine pain scores and OMEs during POD 0, 1, 2, and 3

Post-op visits 1,2, 3, and 4- Pain scores, WOMAC questionnaire scores, and opioid usage amounts collected

Sample Size Calculation:

1. LOS: 2.97 days (controls)-To detect a difference of .5 days (from 2.47 to 2.97, assuming the Exparel group has lower LOS), you need at least 41 patients per group if you assume a homogeneous population and 64 patients per group if you expect there to be greater heterogeneity.
2. NRS Pain score: 6 (controls)-To detect a difference of 1.41 points (from 4.59 to 6.00, assuming the Exparel group has lower pain), you need at least 22 patients per group if you assume a homogeneous population and 53 patients per group if you expect there to be greater heterogeneity
3. WOMAC: 21.5 point difference between pre op and post op score (expect a bigger difference in Exparel group)-To detect a difference of 15 points (21.5 for controls, 36.5 for Exparel patients), you need at least 11 patients per group if you assume a homogeneous population and 17 patients per group if you expect there to be greater heterogeneity.

Outcomes: WOMAC outcome scores (taken pre-operatively, and at 1 week post-operative visit, 2 week post-operative visit, 4 week post-operative visit, and 6 week post-operative visits), NRS Scores (taken on every hospital day and post-operative visit), Opioid Use (inpatient and outpatient), Hospital LOS, and hospital outcomes (complication, inpatient rehab, and readmission rates)

Analysis: Categorical and ordinal variables will be compared using Chi Squared and Fischer's Exact tests as appropriate, while numerical variables will be analyzed using Mann-Whitney-U tests. (IBM SPSS Version 23 Statistics for Windows, Armonk, NY: IBM Corp). For all analyses, $p < 0.05$ denotes statistical significance.

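### Methods restricts complications and readmissions by judged cause while Outcomes does not, and no visit is set up to collect the side effects the protocol names

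*Combined protocol and SAP*

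**What the plan says.** Methods ends with a chart review: "We will finally review EPIC encounter for length of admission (date of admission to date of discharge"), followed by "complication rates from the block, and readmission for pain". Both event types carry a cause, and EPIC is the only source named for them.

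Outcomes lists "hospital outcomes (complication, inpatient rehab, and readmission rates") with no cause attached and no method of collection.

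Risks and Benefits of Exparel states "Risks-side effects of Exparel include N/V, HA, and dizziness", and adds that "more serious risks may include local anesthetic toxicity (neurologic and cardiac symptoms, cardiac arrest").

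Study Visits sets out what is collected at each contact:

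- PACU: "We will visit the patient in PACU to ask about pain scores and determine amount of opioid IV used in PACU".
- POD 1: "We will also visit the patient in POD 1 to discuss expectations of pain control".
- Later visits: "Post-op visits 1,2, 3, and 4- Pain scores, WOMAC questionnaire scores, and opioid usage amounts collected".

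On blinding, Methods says that the patient and the orthopaedic department are blinded and that only the anesthesiologist knows which drug was used.

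**The concern.** In a randomised comparison the arms can be compared on all events, and nobody has to decide what caused each one. Screening events by judged cause before comparing the arms gives up that advantage and puts a subjective step between the event and the count.

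The step matters here because nausea, headache and dizziness have competing explanations in these patients. Under Methods everyone receives a spinal anesthetic and a propofol infusion, and opioid use is expected in both arms. Whether such a symptom is charted as block-related depends on who is judging. The plan neither names that person nor requires that the person be blinded.

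At stake is the balance of the report. The protocol sets out expected benefits in opioid use, pain and length of stay. If the Methods wording is followed, the matching harm comparison could be incomplete, and a reader could not tell whether a low complication rate means few events or few attributed events.

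**Working it through.** The documents state no complication, side-effect or readmission rate. The sample size calculations cover only length of stay, NRS pain and WOMAC. There is therefore no figure to reproduce, and the check is mainly of text.

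**1. The two definitions side by side**

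| Item | Methods | Outcomes |
|---|---|---|
| Complications counted | block-related | any |
| Readmissions counted | pain-related | any |
| Source | EPIC review | not stated |
| Definition of complication | none | none |
| Readmission window | none | none |
| Who judges cause, and whether blinded | not stated | not applicable |

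The sections disagree on what is counted, and only Methods gives a procedure.

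**2. Named risks against planned collection**

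The protocol names nausea or vomiting, headache, dizziness and local anesthetic toxicity. The PACU entry covers pain and IV opioid, the POD 1 entry covers expectations of pain control, and the four later visits cover pain, WOMAC and opioid use. None lists a named side effect, another adverse event or a readmission. Methods does use patient interview as a source for early mobilization, but not for harms.

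**3. What partial recording would do (assumed rates)**

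Inputs: 100 per arm (Methods); alpha 0.05 (Analysis), taken as two-sided because sidedness is not stated; true rates of 20% and 35% in the two arms (assumed); a share c of events recorded, equal in both arms (assumed).

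Power = Φ[(d − 1.96·s0)/s1], where d = c(0.35 − 0.20), s0 = √(2·p̄(1 − p̄)/100), s1 = √((p1(1 − p1) + p2(1 − p2))/100), p1 = 0.20c, p2 = 0.35c, and p̄ is the mean of p1 and p2.

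For c = 1: p̄ = 0.275, s0 = 0.0631, s1 = 0.0622, so (0.15 − 0.1238)/0.0622 = 0.42 and power is 66%.

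| Share recorded | Recorded rates | Recorded difference | Power |
|---|---|---|---|
| 100% | 20% vs 35% | 15 points | 66% |
| 75% | 15% vs 26.25% | 11.25 points | 50% |
| 50% | 10% vs 17.5% | 7.5 points | 34% |
| 25% | 5% vs 8.75% | 3.75 points | 18% |

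The same formula for readmission at an assumed 4% versus 10% gives 38% power with full recording and 21% with half recorded.

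Equal partial recording leaves the ratio unchanged (35/20 = 1.75 in every row) but shrinks the absolute difference. Unequal recording is worse. With a true rate of 20% in both arms, recording 50% in one and 25% in the other gives 10% versus 5%, a difference made entirely by attribution. These figures show direction only.

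**The case against.** The strongest reply is that Outcomes lists both rates unrestricted, Analysis provides tests for all categorical variables, and nothing gives the Methods sentence precedence. All of that is true. A reader might infer that events are counted only when attributed, so that the named side effects are lost from the comparison. The documents do not support that. Complication is undefined, and someone following this protocol could count nausea or dizziness even under Methods, because the protocol itself calls them side effects of the drug. They are neither included nor excluded.

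A reader might also infer that readmissions to other hospitals are lost. That depends on what EPIC shows, which the documents do not describe. It is an open question, and no difference between arms is shown.

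Nor do the documents say that the unblinded anesthesiologist judges cause. A blinded orthopaedic reviewer fits the text equally well. The gap is that the role is unassigned.

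Pain-related readmission is a defensible endpoint given the trial's purpose, which is a reason to keep it as a secondary classification.

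Finally, the trial has limited power for harms in any case. An assumed, fully recorded 35 of 100 versus 25 of 100 gives z = 0.10/√(2 × 0.30 × 0.70/100) = 0.10/0.0648 = 1.54, p about 0.12. That stands. The gain from fuller recording lies mainly in an honest estimate of the difference, less in reaching significance.

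What survives all of this is the contradiction between the two sections, the missing rule for judging cause, and the absence of any visit item for the named risks.

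**Conclusion.** The point holds as an inconsistency with a practical consequence. Methods and Outcomes define different complication and readmission outcomes, and the only operational text is the one that filters by cause. Following it would place an unassigned, possibly unblinded judgement ahead of the randomised comparison, and the named side effects may be missed because no contact is set up to record them.

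The size is unknown, because the documents give neither event rates nor the share of events that would be attributed. The 66% to 18% range above rests on assumed rates, equal recording in both arms and a two-sided test. It is not a prediction. The text does not establish that side effects or outside readmissions are in fact excluded. This is a cheap improvement to measurement and leaves treatment unchanged.

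**What to change.** Bring Methods into line with Outcomes:

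- Count all complications and all-cause readmissions in both arms through the 6-week visit, and state that window.
- At the PACU and POD 1 visits, use the same short checklist in both arms for nausea or vomiting, headache, dizziness and suspected local anesthetic toxicity.
- At the 1, 2, 4 and 6 week visits, ask about admission to any hospital, since the documents do not say whether EPIC shows outside admissions.
- Keep block-related and pain-related as secondary classifications, made by a member of the orthopaedic team, which is already blinded.

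The chi-squared and Fisher's exact tests in Analysis can be used for these counts as they stand.

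Cost: one wording change, a short checklist and a few minutes at each visit already scheduled. Reported event rates will be higher in both arms, and the report should explain why.

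### The exclusions have no cut-off at the study block, so, read literally, a block reaction that stops the TKA removes the patient from the block complication rate

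*Combined protocol and SAP*

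**What the plan says.** **Order of events.** Methods gives each patient an adductor canal block and an iPACK block and says "These blocks will be placed in the pre-operative holding area under ultrasound guidance". The spinal follows: "Intraoperatively, patients will receive a spinal anesthetic utilizing 0.75% hyperbaric bupivacaine". Study Visits agrees, under the day of surgery: "Adductor canal block placed preoperatively". Study drug is therefore in the patient before the spinal and before the TKA. The order of the two blocks is not stated.

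**Exclusions.** Exclusion Criteria begins "Not undergoing a TKA after initially signing up for surgery, if they do not undergo spinal analgesia (due to medical contraindications or a failed attempt" and continues with "if the proper suspension or local anesthetic mixture is not utilized for the block due to physician error" and with voluntary withdrawal at any time in the study. The inclusion criterion also requires that the patient undergo a one-sided primary TKA.

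**Outcome.** Methods plans an EPIC review that covers "complication rates from the block, and readmission for pain". Outcomes lists complication rates among the hospital outcomes, and Analysis assigns categorical variables to Chi-squared or Fisher's exact tests at p < 0.05.

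**Foreseen harm.** The section on risks and benefits says "more serious risks may include local anesthetic toxicity (neurologic and cardiac symptoms, cardiac arrest".

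The documents define no safety population and no denominator for block complications. They do not say how a complication in an excluded patient is handled.

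**The concern.** A complication rate for a block should cover everyone who was given the block. Here the exclusions stay open after the injection, and some can be triggered by the complication itself. Toxicity in the holding area could cancel the operation. The patient has then not undergone a TKA after signing up for one, and meets an exclusion because of the event that the rate is meant to count.

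The events most exposed are the severe ones, since a mild reaction would not stop surgery. An arm could be reported with no block toxicity when one case had occurred. That matters for a trial whose document names cardiac arrest as a possible risk, and the rate is a listed outcome to be compared between arms.

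**Working it through.** **Step 1. Which exclusions can follow the block, and which can a block reaction cause?** The timing comes from Methods, Study Visits and Exclusion Criteria.

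| Exclusion | Can apply after the block? | Can a block reaction cause it? |
|---|---|---|
| No TKA | Yes; it runs from sign-up with no end point | Yes, if the operation is cancelled |
| No spinal, medical contraindication | Yes | Possibly, but a pre-existing reason is at least as natural a reading |
| No spinal, failed attempt | Yes; the attempt comes after the block | No |
| Wrong mixture | Triggered at the block itself | No, but any complication in that patient goes too |
| Voluntary withdrawal | Yes | Possibly |

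A cancellation before any block costs nothing, because there was no exposure. Toxicity in a patient who goes on to spinal and TKA and stays in the study, after a correctly prepared block, is still counted.

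**Step 2. Effect of one lost event.** The arm size of 100 is from Methods. The exact (Clopper-Pearson) 95% limits for x events in n are the 0.025 quantile of Beta(x, n−x+1) and the 0.975 quantile of Beta(x+1, n−x). For x = 0 the lower limit is 0 and the upper limit is 1 − 0.025^(1/n).

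| Situation | All blocked patients | After exclusion |
|---|---|---|
| Patient not replaced | 1/100: 0.03 to 5.45% | 0/99: 0 to 3.66% |
| Patient replaced to reach 100 | 1/101: 0.03 to 5.39% | 0/100: 0 to 3.62% |

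For example, the upper limit for 0/99 is 1 − 0.025^(1/99) = 3.66%. With more events the rate falls but does not vanish: 5/100 = 5.0% with two patients removed becomes 3/98 = 3.1%.

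**Step 3. Effect on the planned test.** With one event among 200 patients in equal arms, the event falls in either arm with probability 1/2, so the two-sided Fisher p is 1/2 + 1/2 = 1. With the event removed and none in the other arm, there is nothing to test. At this count the damage is to the reported number of events, not to a significance call.

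**Step 4. Chance that it happens.** The documents give no toxicity rate p and no share f of events that lead to removal. Both are assumptions here. The chance of losing at least one event among 200 blocked patients is 1 − (1 − p·f)^200.

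| p | f = 0.1 | f = 0.25 | f = 0.5 |
|---|---|---|---|
| 0.05% | 1.0% | 2.5% | 4.9% |
| 0.1% | 2.0% | 4.9% | 9.5% |
| 0.5% | 9.5% | 22% | 39% |
| 1% | 18% | 39% | 63% |

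For the wrong-mixture route, assume 4 such patients and a block complication rate q. The chance of losing at least one complication is 1 − (1 − q)^4: 0.4%, 3.9% and 19% for q = 0.1%, 1% and 5%.

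**The case against.** **No rule discards these events.** This stands. A reader might infer that the plan throws away complications in excluded patients. No sentence says so, and the EPIC review could still find them. The point is narrower: excluding a patient ordinarily takes that patient out of the rates, and nothing exempts this rate. Finding an event is not the same as counting it.

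**The groups are already the blocked patients.** Methods "will collect 100 patients who receive an adductor canal block with Exparel" and a matching ropivacaine group, which could be read as an all-blocked denominator. It does not settle the matter. A patient whose spinal attempt fails has normally had the block by then and is still expressly excluded, so receiving the block does not by itself keep a patient in.

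**The spinal route is strained.** Largely accepted. A reaction bad enough to rule out the spinal would often stop the TKA as well, so this route adds little. The no-TKA exclusion carries the point.

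**The probabilities rest on invented rates.** Also accepted. The table in Step 4 shows only how the chance depends on two unknowns. What does not depend on them is the arithmetic in Step 2.

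**Conclusion.** The point holds as a gap in wording with a definite mechanism. The exclusions stay open after the block, some can be set off by a block reaction, and no safety exception is stated. One lost event changes 1/100 (0.03 to 5.45%) to 0/99 (0 to 3.66%).

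This rests on the literal reading of exclusion and on at least one such event occurring. The chance of that cannot be found from the documents. It is probably small, but that is a judgement. If toxicity is as rare as the top rows of the Step 4 table, the gap would most likely never operate.

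Two stronger conclusions are tempting and not supported. One is that the trial's complication rates will be understated: the documents show only that they could be. The other is that the loss favours one arm: neither its size nor its direction by arm can be worked out from the plan.

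The same exclusions also take patients out of the efficacy comparisons after allocation. That is a separate question and is not judged here. The point merits consideration because the change costs so little, not because harm is likely.

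**What to change.** Add to Exclusion Criteria and Analysis:

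> No exclusion criterion, and not the requirement to undergo TKA, removes a patient from the block complication analysis. Block complications are reported and compared as n/N in every randomised patient in whom injection of any study block (adductor canal or iPACK) was started, whether or not the spinal or TKA followed. For patients who withdraw, data up to withdrawal are used. Patients are grouped by adductor canal drug received (Exparel if any Exparel was injected), or by randomised arm if no adductor canal injection was given. Mixture errors, and patients whose spinal or TKA did not follow the block or who withdrew, are listed by arm with the reason.

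The wording covers withdrawal and the TKA inclusion requirement because either could otherwise remove the same patient. It starts at the first injection of either block because, if the iPACK block came first, a reaction to it could stop the procedure before the adductor canal injection.

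The cost is one paragraph, one table row and short listings, drawn from EPIC encounters already due for review. The downside is that the safety denominator will differ slightly from the efficacy denominator, which a footnote can explain.

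### If the planned 2.47-day mean stay is met and LOS is in whole days, at least 17.7% of Exparel patients (26.5% if every stay is at least 1 day) have no POD 3 EPIC record, and home opioid use is not tied to POD 0-3

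*Combined protocol and SAP*

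**What the plan says.** Methods sets the window without limiting it to inpatients: "Pain scores and OMEs will be calculated for POD 0-3". Study Visits names the source: "We will also look in EPIC to determine pain scores and OMEs during POD 0, 1, 2, and 3". For POD 0 there is also a bedside source: "We will visit the patient in PACU to ask about pain scores and determine amount of opioid IV used in PACU". The POD 1 visit is described as a discussion, not as a data collection: "We will also visit the patient in POD 1 to discuss expectations of pain control".

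Outcomes places NRS on hospital days and at post-operative visits, which fall at 1, 2, 4 and 6 weeks. It lists opioid use as both inpatient and outpatient. For visits 1 to 4, Study Visits says: "Pain scores, WOMAC questionnaire scores, and opioid usage amounts collected". Nothing says how opioid use at home is assigned to days, or whether it enters the POD 0-3 figure.

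LOS is defined in Methods: "We will finally review EPIC encounter for length of admission (date of admission to date of discharge"). Sample Size Calculation, item 1, plans 2.97 days for controls and 2.47 for Exparel. Risks and Benefits of Exparel aims for "<60 oral morphine equivalents during first 2-3 days" and to "decrease length of hospital stay (by 0.5-1 day"). Analysis gives Mann-Whitney tests for numerical variables and no rule for missing values.

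**The concern.** Lower opioid use, lower pain scores and a shorter stay are three of the four aims in Purpose. A hospital record stops at discharge, so the third aim, if met, removes data from the first two.

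Two things are at stake. First, a POD 3 comparison of NRS or OME is made among patients still in hospital. That subset is selected by an outcome the block is meant to change, so randomisation no longer protects the comparison. Second, if OME is totalled over POD 0-3 from EPIC alone, the arm that goes home earlier has fewer countable days and can show a lower total with no analgesic effect. The opioid target is ambiguous at the same place: a window of 2-3 days lies mostly within the stay if read as POD 0-2, but not if it runs to POD 3.

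**Working it through.** **Inputs.** From the documents: planned LOS 2.47 (Exparel) and 2.97 (control), read as means; LOS as discharge date minus admission date; 100 patients per arm; 41 or 64 per group for the LOS comparison. Assumption: surgery is not before admission. A POD 3 record, even a partial one on the day of discharge, then needs LOS of at least 3. Surgery after the admission date would only raise the share without a record.

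**The plan's own LOS figure.** SD, power and sidedness are not stated. With two-sided 5% and 80% power, n = 2 × (1.960 + 0.842)² × SD² / 0.5². SD 0.8 gives 40.2, so 41. SD 1.0 gives 62.8, so 63, or 64 by the t-test. The stated 41 and 64 are therefore consistent with SDs of about 0.8 and 1.0, which are back-solved and not documented.

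**Bound from the mean alone, whole-day LOS.** If the shortest stay is m days, mean ≥ m + (3 − m) × P(LOS ≥ 3). The share without a POD 3 record is therefore at least 1 − (mean − m)/(3 − m).

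| Shortest stay | Exparel, mean 2.47 | Control, mean 2.97 |
|---|---|---|
| 0 days | 1 − 2.47/3 = 17.7% | 1 − 2.97/3 = 1.0% |
| 1 day | 1 − 1.47/2 = 26.5% | 1 − 1.97/2 = 1.5% |

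Days on record out of the four are 1 + min(LOS, 3), at most 1 + LOS. On average at least 3 − 2.47 = 0.53 days per Exparel patient fall after discharge.

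**If LOS is fractional.** Suppose POD 3 begins t days after admission, with t assumed between 2.6 and 2.8. The bound becomes 1 − (2.47 − m)/(t − m). With m = 0 it is 5.0% to 11.8%; with m = 1 it is 8.1% to 18.3%. The range is about 5-18%.

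**POD 2.** The means give no such bound here. A mean of 2.47 is compatible with every patient staying at least 2 days (53% staying 2 days, 47% staying 3).

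**Difference between arms.** These are lower bounds, so 26.5% against 1.5% is not an estimate of the difference. Adding SD 1.0 and a 1-day minimum, the share with a POD 3 record can be as high as about 73% for Exparel and as low as 48.5% for control, so the ranges overlap.

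**Illustration only** (normal LOS, SD 0.8 or 1.0, POD 3 record if LOS exceeds 2.5, earlier days cut at 0.5 and 1.5):

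- POD 3 record: about 49% Exparel, 68-72% control.
- POD 2 record: 83-89% Exparel, 93-97% control.
- EPIC-only OME total, no analgesic effect, equal use each day: 3.37 against 3.69 recorded days (SD 0.8), or 8.7% lower on Exparel; 3.30 against 3.60 (SD 1.0), or 8.5% lower.
- With use falling over the days in the ratio 1/1/0.5/0.25, the gap is 3.9-4.3%. Hence about 4-9%.
- Moving the POD 3 cut between 2.0 and 3.5 days widens this to 2-16%.

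**The case against.** The strongest reply is that the plan never says OME will be summed, nor that days after discharge count as zero. Study Visits lists the days one by one. Analysed per day, discharged patients simply have no POD 3 value and the counting artefact does not arise. This stands: the fault is an undefined summary, and the 4-9% applies only to one way of filling it in.

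Second, a reader might infer that home opioid use is not collected. The documents do not support that. Outcomes includes outpatient use and every post-operative visit records amounts. What is missing is a rule tying that use to POD 0-3.

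Third, a reader might infer that the plan's figures establish unequal POD 3 loss between arms, or a pain bias of known direction. They do not. The arm contrast needs assumed SDs and normality, and any NRS bias also needs a relation between pain and stay that the plan does not document. It is zero if the two are unrelated, and runs against Exparel if sorer patients stay longer in the same way in both arms.

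Fourth, setting the 1-day reduction against the control figure gives 2.97 − 1 = 1.97 days and bounds of 34.3% and 51.5%. No passage states a 1.97-day mean, and joining a hoped-for range to a sample size input is too loose a basis for the headline.

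Finally, the restriction of NRS to hospital days could be read as a deliberate limit on the POD 0-3 window. It may be, but then the POD 3 comparison is among inpatients by design, and the selection problem remains.

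**Conclusion.** The point holds in conditional form. If the planned mean Exparel stay is met and LOS is in whole days, at least 17.7% (same-day discharge possible) or 26.5% (every stay at least 1 day) of that arm have no POD 3 record. If LOS is fractional, the bound is about 5-18%. The date-to-date definition favours whole days but does not settle it.

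POD 3 NRS and OME would then be compared in a subset formed after randomisation. That subset may differ by arm if the block shortens stay, but the means alone do not show this. The opioid artefact is contingent on summing EPIC use and letting days after discharge contribute nothing.

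LOS, WOMAC and clinic-visit NRS are unaffected, and nothing here justifies setting POD 2 aside. The matter should be fixed because it bears on two stated aims and the remedy is small.

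**What to change.** - **Opioid use.** Define POD 0-3 OME as inpatient OME from EPIC plus home opioid use through POD 3, asked at the existing 1-week visit. State that days after discharge are not counted as zero. Treat patients who cannot supply home use as missing and report their number by arm. Say which days the 2-3 day target covers.
- **Pain.** Report POD 2 and POD 3 NRS with the number in hospital by arm. Keep POD 0-2 for the between-arm comparison, with the POD 2 denominators shown, and treat POD 3 inpatient NRS as descriptive.
- **LOS.** State whether it is recorded in whole days.

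The cost is a change of wording and one question at a visit already scheduled. The downsides are recall error for home use and no formal POD 3 NRS test. To keep that test, the sponsor would have to obtain POD 3 scores from discharged patients. With 100 per arm and every stay at least 1 day, that is at least 26.5 + 1.5 = 28 of 200 patients if the planned means are met.

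### The text names no pre-operative value for opioid use or NRS and plans unadjusted tests, which leaves precision unused, mainly for opioid use

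*Combined protocol and SAP*

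**What the plan says.** - **Aims.** The Purpose lists four aims in one sentence. The first two are "reduce opioid requirement use postoperatively, reduce pain scores postoperatively". None is designated primary.
- **Timing of NRS and opioid use.** Outcomes lists "NRS Scores (taken on every hospital day and post-operative visit), Opioid Use (inpatient and outpatient". Methods adds "Pain scores and OMEs will be calculated for POD 0-3", and Study Visits adds the PACU and four post-operative visits. All of these fall on or after the day of surgery.
- **Timing of WOMAC.** This is the only outcome with a named baseline: "WOMAC outcome scores (taken pre-operatively, and at 1 week post-operative visit".
- **Pre-op visit.** Study Visits has the "Patient seen in Ortho office for initial consent to TKA and to fill out questionnaire (see attached"). The attachment is not in the text available for review.
- **Eligibility.** Inclusion is "Undergoing unilateral primary TKA for a diagnosis of knee osteoarthritis" with no concomitant procedure. Neither the inclusion nor the exclusion criteria mention prior opioid use.
- **Analysis.** "numerical variables will be analyzed using Mann-Whitney-U tests". Categorical and ordinal variables go to chi-squared or Fisher's exact tests. No covariate, change score or regression model is named for any outcome.
- **Sample size.** Calculations are given for LOS, NRS and WOMAC. For opioid use there is only a target below 60 OME, with no control mean, SD or difference.

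**The concern.** Patients who already take opioids and patients who do not can both enrol. Part of the spread in post-operative OME will reflect that difference rather than the block. A baseline value could remove some of that spread, but the text names none, and the planned test could not use one. The same holds for NRS.

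What is at stake is efficiency. Opioid use heads the list of aims, the plan itself expects only a modest reduction, and no calculation shows what 100 per arm can detect. It is the outcome with the least demonstrated margin, so a cheap gain in precision is worth most there.

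**Working it through.** **Inputs from the document:** 100 per arm (Methods); significance at 0.05, sidedness not stated (Analysis); NRS difference 1.41 points with 22 or 53 per group (Sample Size Calculation).

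**Assumed, because the document gives no value:** two-sided 0.05, 80% power, the baseline/outcome correlation r, and the share of prior opioid users.

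**1. The plan's NRS figure.** SD and power are not stated, so 22 and 53 cannot be reproduced directly. The SD can be back-solved from n = 2 × SD² × (1.960 + 0.842)² / 1.41², that is, SD = 1.41 × √(n/2) / 2.802.
- n = 53: 1.41 × 5.148 / 2.802 = 2.59.
- n = 22: 1.41 × 3.317 / 2.802 = 1.67.

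Both are plausible on a 0–10 scale. The stated sizes are unverifiable but not shown to be wrong.

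**2. NRS power at 100 per arm, unadjusted.** With SD 2.59, the standard error is 2.59 × √(2/100) = 0.366. Then 1.41/0.366 = 3.85 and Φ(3.85 − 1.96) = 97%. With SD 1.67 the power exceeds 99.9%. Adjustment at r = 0.5 would raise the 97% to 99.4%. NRS therefore has ample margin already, and its gain is a narrower interval.

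**3. Opioid use, unadjusted.** With no SD in the plan, only a standardised figure is possible: 2.802 × √(2/100) = 0.396 SD at 80% power. This is for a comparison of means. For normal data, Mann-Whitney (relative efficiency 0.955) gives 0.405 SD. For skewed OME its relative efficiency would differ, and it was not computed.

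**4. Effect of adjustment.** In a linear model with a baseline covariate, the residual variance is multiplied by 1 − r². Equivalent n is 100/(1 − r²), and the detectable difference is 0.396 × √(1 − r²). The last column is power at an assumed effect of 0.3 SD.

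| r (assumed) | Variance cut | 100 per arm behaves like | Detectable difference | Power at 0.3 SD |
|---|---|---|---|---|
| 0 | 0% | 100 | 0.40 SD | 56.4% |
| 0.2 | 4% | 104 | 0.39 SD | 58.1% |
| 0.3 | 9% | 110 | 0.38 SD | 60.4% |
| 0.5 | 25% | 133 | 0.34 SD | 68.8% |
| 0.6 | 36% | 156 | 0.32 SD | 75.5% |

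**5. What yes/no prior use could deliver.** Let a share p use opioids before surgery, and let users' OME be g within-group SDs higher. Then r = g√(p(1−p)) / √(1 + g²p(1−p)). With p = 0.25 (assumed), p(1−p) = 0.1875.
- g = 0.5: r = 0.2165/1.0232 = 0.21, and 100 behaves like 105.
- g = 1: r = 0.4330/1.0897 = 0.40, and 100 behaves like 119.
- r = 0.6 needs g² = 0.5625/0.1875 = 3, so g is about 1.7.

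Daily OME may add information, but if 25% are users, most values are zero.

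**6. Chance imbalance.** With p = 0.25, the SD of the difference in user share between arms is √(2 × 0.25 × 0.75/100) = 0.061. A gap of 10 percentage points or more therefore arises in about 10% of trials. With g = 1, such a gap moves the arm difference by 0.10 SD. The standard error is 1.0897 × √(2/100) = 0.154 SD, so the shift is about 0.65 standard errors, which is ordinary sampling variation.

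**The case against.** The strongest reply is that the plan contains no error here. The trial is randomised, so the unadjusted comparison is valid. A reader might infer that a chance excess of prior users in one arm would bias the result, but the standard error and p-value already allow for it, as step 6 shows. This part of the objection stands in full.

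Three further parts stand as limits on the point.
- A reader might infer that no baseline is collected at all. The pre-op questionnaire is not shown and may hold pain or opioid items, so the text supports only the statement that none is named.
- A reader might take NRS to be short of power. The plan's own NRS calculation, set against 100 per arm, says otherwise.
- The size of the gain for opioid use rests wholly on assumed correlations. At r = 0.2 or below it is negligible, and yes/no prior use alone is unlikely to reach the top of the range.

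It may also be said that NRS is not clearly assigned to Mann-Whitney, since ordinal variables go to chi-squared or Fisher tests and NRS is not classified. That is correct, but neither route takes a covariate. If the questionnaire does hold the baseline items, the collection half of the point is met and the unadjusted analysis remains.

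**Conclusion.** The point holds as a loss of precision. No pre-operative opioid or NRS value is named in the text, and the tests named cannot use one. For opioid use, adjustment would make 100 per arm behave like about 104 to 156, and the detectable difference for a comparison of means would fall from 0.40 SD to between 0.39 and 0.32 SD. This assumes correlations of 0.2 to 0.6, two-sided 0.05 and 80% power. The lower part of that range is the likelier one if only yes/no prior use is recorded. For NRS the practical gain is small, because power for 1.41 points is already about 97% under the larger back-solved SD.

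The documents do not support calling the planned comparison biased or invalid. Nor do they support calling opioid use the primary outcome: it is listed first among four aims, and none is ranked. The change is worth making because the visit already exists and the outcome that gains most has no sample-size calculation.

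**What to change.** **Data.** At the existing pre-op visit, before the block, record current opioid use (yes/no, and daily OME from the EPIC medication list) and NRS, unless the attached questionnaire already does. Name these time points in Outcomes.

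**Analysis.** Pre-specify the following:
- In-hospital OME is analysed by a linear model on ranks, with arm and baseline opioid use as terms. Ranks cope with zero OME, which a log transformation does not.
- NRS is analysed by a linear model with arm and baseline NRS. If baseline NRS is not available, pre-operative WOMAC, which is already collected, is the fallback covariate.
- The unadjusted Mann-Whitney test is kept as the sensitivity analysis for both.

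**Cost.** One or two extra items at a visit that already takes place, a few sentences in Outcomes and Analysis, and an occasional missing covariate. Eligibility, treatment and sample size do not change.
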